A complete physical exam of the following systems will be performed by the investigator or appropriately qualified designee and documented in the source and in the eCRF at Screen, Day 7 and Day 14. A complete physical examination, performed at screening and other specified visits, should include an evaluation of the head, eyes, ears, nose, and throat, and the cardiovascular, dermatologic, respiratory, gastrointestinal, and neurologic systems. Any abnormality identified at baseline should be recorded in the patient's medical records. Limited, symptom-directed physical examinations should be performed at specified postbaseline visits and as clinically indicated. Changes from baseline abnormalities should be recorded in patient notes. New or worsened clinically significant abnormalities should be recorded as adverse events in the patient's medical records.

Vital Signs

Vital signs, including blood pressure (BP), temperature and heart rate will be collected and documented in source and in the eCRF.

Pulse and Walking Oximetry

SpO2 and 6-minute walk test (walking oximetry) will be performed at screening.

Height and Weight

Height and weight of patient will be taken at screening.

Laboratory Evaluations (Hematology and Serum Chemistry)

Blood samples (approximately 10 ml in total) will be taken for the following laboratory evaluations: Albumin, alkaline phosphatase, total bilirubin, direct bilirubin, bicarbonate, BUN, calcium, chloride, creatinine, glucose, LDH, phosphorus, potassium, total protein, AST, ALT, sodium, CBC/diff, LDH, , CRP, prothrombin time, activated partial prothrombin time, D-dimer

Pregnancy Test

Females of child-bearing potential will have a serum pregnancy test completed.

Baseline Visit

The following evaluations should be completed at the Baseline visit:

Inclusion/Exclusion Criteria Evaluation

Participants will be re-assessed to ensure that they meet all inclusion criteria and do not meet any of the exclusion criteria as listed in sections 5.1 and 5.2

Vital Signs

Vital signs, including blood pressure (BP), temperature and heart rate will be collected and documented in source and in the eCRF.

Sample for quantitative viral load testing (RT-PCR) and confirmation of Covid-19 positive result Participants will have a sample taken for RT-PCR quantitative viral testing.

Serum Collection (Immune monitoring)

Blood samples (approximately 15 ml) will be collected for immune monitoring

Randomization

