Participants will be randomized to receive either TQ Formula + Standard of Care (SOC) or placebo +SOC

Administer Study Intervention

Participants will be provided with study treatment kit, with enough capsules for 14 days of treatment, 3 capsules BID.

Concomitant Medications and Adverse Events Review

Participants will be assessed for any new adverse events and any changes in concomitant medications

Patient Reported Outcomes

Participants will receive the Modified FLU-PRO Plus questionnaire to complete on a daily basis for the duration of the study, from randomization to final study visit (Day 21).

Subsequent Study Visits (Including Day 21 Final Visit)

Concomitant Medications and Adverse Events Review

Participants will be assessed for any new adverse events and any changes in concomitant medications at each study visit

Physical Exam

A complete physical exam will be performed by the investigator or appropriately qualified designee and documented in the source and in the eCRF at Day 7 and Day 14. A complete physical examination, performed at screening and other specified visits, should include an evaluation of the head, eyes, ears, nose, and throat, and the cardiovascular, dermatologic, respiratory, gastrointestinal, and neurologic systems. Any abnormality identified at baseline should be recorded in the patient's medical records. Limited, symptom-directed physical examinations should be performed at specified postbaseline visits and as clinically indicated. Changes from baseline abnormalities should be recorded in patient notes. New or worsened clinically significant abnormalities should be recorded as adverse events in the patient's medical records.

Vital Signs

Vital signs, including blood pressure (BP), temperature and heart rate will be collected and documented in source and in the eCRF at each study visit.

Serum Collection (Blood sample for immune monitoring)

Blood samples (approximately 15 ml) will be collected for immune monitoring at Day 7 and Day 14, in addition to the baseline visit.

Sample for quantitative viral load testing (RT-PCR)

Participants will have a sample taken for RT-PCR quantitative viral testing at Day 7 and again at Day 14, in addition to the baseline visit.

Laboratory Evaluations (Hematology and Serum Chemistry)

Blood samples (approximately 10ml in total) will be taken for safety laboratory evaluations (as listed in screening above) at Day 7 and 14 and as clinically indicated at any other study visits

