5 STUDY POPULATION

5.1 INCLUSION CRITERIA

In order to be eligible to participate in this study, an individual must meet all of the following criteria:

1. Provision of signed and dated informed consent form
2. Stated willingness to comply with all study procedures and availability for the duration of the study
3. Male or female, aged 18 and over, presenting with recent mild to moderate clinical symptoms of Covid-19 infection (per FDA guidance – see appendix 3)
4. Positive COVID-19 infection confirmed with a rapid antigen test at screening and confirmed with a RT-PCR test at baseline
5. A score of ≥ 3 on a minimum of 2 symptoms on the Modified FLU-PRO Plus
6. Ability to take oral medication and be willing to adhere to the dosing regimen (Twice a day – BID for 14 days)
7. For females of reproductive potential: negative pregnancy test at screening and use of highly effective contraception method during study participation and for an additional 4 weeks after the end of study drug administration
8. For males of reproductive potential: use of condoms or other methods to ensure effective contraception with partner during study participation
9. Agreement to adhere to Lifestyle Considerations (see section 5.3) throughout study duration

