9.4.2 ANALYSIS OF THE PRIMARY EFFICACY ENDPOINT(S)

The primary endpoint of this clinical trial is the estimate of the median time to sustained clinical response for the treatment and placebo arms. Kaplan-Meier method will be used to estimate the time to sustained clinical response distribution and log-rank test will be utilized to compare the time to sustained clinical response distributions between the two study arms. Events will be defined as cases that attain clinical response while on the follow-up window and time to event will be calculated as the days from symptom onset to the resolution of symptoms to zero based on the Modified FLU-PRO Plus questionnaire. Patients who do not attain to clinical response while on the follow-up window will be censored on Day-21 or on the day they are off study before Day-21 due to other reasons. Although all analyses will be conducted based on the intent-to-treat context, sensitivity analyses based on the adherence to the protocol regimen will also be carried out for the primary as well as secondary objectives.

When appropriate, Last-Value-Carried-Forward (LVCF) imputation approach will be utilized for the missing values. As this is a small study that has a short span of enrollment and treatment windows, we do not anticipate excessive missing values; however, missingness structure will still be analyzed as to whether or not the missingness is Missing Completely at Random (MCAR), or Missing at Random (MAR), or Not-Missing at Random (NMAR). In the even of MCAR and MAR, sensitivity analyses will be carried out by using Multiple Imputation (MI) techniques.

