# BOSS-Covid-19 Study (BOSS-001)

at least three days. Time to sustained clinical response will be calculated from the date of testing to the first day all symptoms are  $\leq 2$ .

Power calculation will be based only on the first primary objective of the trial. Based on the median time to sustained clinical response reported by CDC [122], the expected median time to response in the placebo arm will be approximately 16 days from the onset of symptoms in outpatients. With a sample size of 20 in each arm, a difference in median time to sustained clinical response of 10 days between the intervention arm and the placebo arm will be able to be detected with 81.5% statistical power with 5% Type-1 error rate. Median time to sustained clinical response will be estimated based on 21-day follow-up. With an attrition expectation of around 20%, the planned accrual is 26 patients in each arm and potentially up to 30 patients.

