# BOSS-Covid-19 Study (BOSS-001)

## 5.3.2 Primary Analyses

Primary estimand-1 is defined to be the difference of median time to sustained clinical response between participants taking 3 g TQ Formula (500 mg per capsule, 3 capsules BID) and participants taking placebo regardless of whether or not they actually receive their assigned therapy (ITT) and assuming that their hospitalization and treatment discontinuation rates will be similar. Possible intercurrent events for this estimand can be, though expected to be quite rare, hospitalization (i.e., transitioning from outpatient status to inpatient status) and treatment discontinuation, both of which may lead to potential missing data or change in the primary measures. The study participants will be reminded to submit their Modified FLU-PRO Plus questionnaires even after these intercurrent events to avoid missing data as much as practically possible. Hospitalization-free, while-on-study and per-protocol treatment versions of the above estimand will also be considered within each population definitions above.

Median time to sustained clinical response for the treatment and placebo arms will be estimated using the Kaplan-Meier method and Log-rank test will be utilized to compare the time to sustained clinical response distributions between the two study arms using LIFETEST procedure in SAS Version 9.4 ® (SAS Institute, Cary, North Carolina, USA). Events will be defined as cases that attain sustained clinical response while on study and time to event will be calculated as the days from the date of symptoms onset to the date that all symptoms are below Level-2 ('A little bit') on the Modified FLU-PRO Plus questionnaire. Patients who do not attain to clinical response while on study will be censored on Day-21 or on the day they are off study before Day-21 due to other reasons.

Although all analyses will be conducted based on the intent-to-treat principle, sensitivity analyses based on the adherence to the protocol regimen will also be carried out for the primary as well as secondary objectives. Sensitivity analyses will also include hospitalization-free, while-on-study, and per-protocol treatment cohorts as described above.

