## **6.3 Definitions for Clinical Evaluation**

Clinical evaluation will be done using Flu-Pro Plus questionnaire modified for Covid-19 patients treated in an outpatient setting. The participants will fill out the questionnaire at the time of Screening, Enrollment, and from Day-1 to Day-21 post randomization each day using online data capture forms.

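### The SAP times the primary endpoint from the date of testing in 3.2 and from symptom onset in 5.3.2, and Day-21 censoring is not expressed on either clock

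*SAP*

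**What the plan says.** Two origins are written for the same primary endpoint.

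- SAP 3.2: "Time to sustained clinical response will be calculated from the date of testing to the first day all symptoms are" at or below 2.
- SAP 5.3.2: "time to event will be calculated as the days from the date of symptoms onset".
- Protocol 9.4.2: "time to event will be calculated as the days from symptom onset to the resolution of symptoms to zero". (The different symptom threshold there is a separate matter.)

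A third time frame governs data collection. SAP 6.3 has the questionnaire filled in "from Day-1 to Day-21 post randomization each day using online data capture forms", and Protocol 4.1 gives the same window. Under SAP 5.3.2, patients without a response "will be censored on Day-21 or on the day they are off study before Day-21"; Protocol 9.4.2 has the same rule.

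The sizing text (SAP 3.2, Protocol 9.2) takes a placebo median of about 16 days from symptom onset, a 10-day difference, 20 per arm, 81.5% power and 21 days of follow-up. SAP 3.2 thus measures the endpoint from testing but plans it from onset.

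**The concern.** A SAP should leave one way to compute the primary time variable, and this one leaves at least two. The date of testing is not a single date either. It could be the screening antigen test, which Protocol 4.1 allows before consent, the RT-PCR within the last 3 days that SAP 3.3.1 accepts, or the baseline RT-PCR. No passage says how study Day 21 is expressed on the onset or testing clock.

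The onset clock also contains time in which no event can occur. Entry requires a score of 3 or more "on a minimum of 2 symptoms on the Modified FLU-PRO Plus", and at baseline "Participants will be re-assessed to ensure that they meet all inclusion criteria", so the days between onset and randomization are event-free by design.

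At stake are the reported medians, the estimated difference in the one trial that will be run, and occasionally its significance. SAP 7.7 unblinds the study statistician for the preliminary efficacy report, so a choice made after that point would be open to question.

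**Working it through.** **The plan's own power figure.** With exponential times, HR = 16/6 = 2.667. Expected events with 20 per arm and 21 days of follow-up:

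- placebo 20 × (1 − exp(−ln2 × 21/16)) = 11.9
- active 20 × (1 − exp(−ln2 × 21/6)) = 18.2
- total 30.2

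Schoenfeld power = Φ(√30.2/2 × ln 2.667 − 1.96) = Φ(0.73) = 76.9%. The stated 81.5% is approached if follow-up runs past 21 days for some patients (80.9-81.2% by the Lakatos method with 4-5 weeks of accrual added) or if all 40 patients have the event (82.0% by Freedman). The inconsistency of origins does not depend on this figure.

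**One patient on three clocks (illustration).** Take onset 7 days and the test 1 day before randomization, with response 7 days after randomization. The time is 7 days from randomization, 7 + 1 = 8 from testing and 7 + 7 = 14 from onset. Day 21 is 20 days after Day 1, so a non-responder is censored at 20, 21 or 27 days.

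**Simulation inputs.** The HR of 2.667 follows from the plan's 16 and 6 days, and the 26 per arm is its planned accrual. The rest is assumed, because the documents give no lag:

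- onset-to-randomization lag uniform over 1-5, 1-10 or 1-14 days (means 3, 5.5, 7.5)
- test-to-randomization gap uniform over 0-3 days, never above the lag
- HR 1, 2 and 2.667; 21 days of follow-up from randomization; times rounded to days
- Model A: exponential from randomization, placebo median 16 minus the mean lag
- Model B: Weibull with shape 2 from onset, median 16, conditional on no response before entry

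There were 4,000 trials per scenario (Monte Carlo SE at most 0.8 point). Each was analysed by Kaplan-Meier and a two-sided 5% log-rank test, with censoring converted to the clock in use.

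| Lag (days) | Arm median, onset minus testing clock | Log-rank verdict differs | Power, testing vs onset, Model A (HR 2; HR 2.67) | Same, Model B |
|---|---|---|---|---|
| 1-5 | 1.7-1.8 days | 3-7% | 60.5 vs 59.6%; 88.1 vs 88.0% | 61.7 vs 62.7%; 90.8 vs 91.2% |
| 1-10 | 4.2-4.6 days | 5.5-12% | 61.3 vs 59.5%; 89.7 vs 87.4% | 62.7 vs 65.2%; 89.4 vs 91.4% |
| 1-14 | 6.4-6.9 days | 10-18% | 64.9 vs 57.0%; 90.6 vs 83.1% | 59.6 vs 62.5%; 88.6 vs 89.7% |

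The mean difference in medians moves by at most 0.5 day between clocks, against a trial-to-trial SD of 2.3-3.7 days. Type I error on each single clock is 5.0-6.0%.

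A separate simulation (Model A, HR 2, 1,500 trials per scenario) gave placebo medians of 14.9 vs 16.6, 12.8 vs 17.0 and 10.6 vs 17.3 days (testing vs onset), with verdicts differing in 4%, 10% and 18% of trials.

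**Moving the sizing to randomization.** Subtracting the mean lag L from 16 and 6 days:

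- L = 3: 13 and 3 days
- L = 5.5: 10.5 and 0.5 days
- L = 7.5: 8.5 and −1.5 days

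The active median, 6 − L, is not positive once L reaches 6. If HR 2.667 is held instead, with placebo median 16 − L, Schoenfeld power at 20 per arm over 21 days is 76.9% (L = 0), 79.8% (L = 3), 81.7% (L = 5) and 83.5% (L = 7).

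**The case against.** The best defence is that SAP 5.3.2 is the operative analysis section, the protocol's analysis section agrees with it, and the planning median is also from onset. The testing sentence then looks like a slip in a sample-size paragraph. Censoring on Day 21 most naturally names a calendar day, from which a programmer would subtract the onset date. This makes keeping onset a legitimate repair. It does not remove the conflict, because SAP 3.2 is an explicit derivation rule and no order of precedence is given.

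Other points that stand:

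- The supplied protocol may predate the Version 6.0 that SAP 2.2 cites, since it lacks items the SAP carries (for example, the three-day requirement in the response definition). The firm contradiction is therefore SAP 3.2 against SAP 5.3.2.
- Entry requires recent symptoms, though no number of days is given, so lags up to 14 days may be pessimistic.
- Some disagreement arises from any small shift of clock. The testing and randomization clocks disagree on significance in about 2-6% of trials, so the 3-7% at lag 1-5 is little more than that background.
- The simulations hold the hazard ratio fixed, not the 10-day difference. In a rerun at HR 2.67 the mean difference in medians was 4.8-7.6 days.

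A reader might infer more: that the double definition inflates type I error, or that non-responders will be coded as 21 on the onset clock and power lost. The first requires keeping the smaller of two p-values, which no passage allows. The second requires a coding step that no passage states. Both are hypothetical and are left out of the size given here.

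**Conclusion.** The concern holds as a contradiction between two written rules for the primary time variable, with no rule for placing Day 21 on either clock. It should be fixed. Under the assumed lags, arm medians shift by about 2, 4 or 6-7 days between the written clocks, and the log-rank verdict changes in roughly 3-7%, 5-12% or 10-18% of trials.

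The documents do not support a charge of bias. The average difference in medians is almost unchanged, each single clock holds its error rate near 5%, and both arms are treated alike. Power differs materially only with long lags and a hazard that starts at randomization: at lag 1-14 and HR 2, onset is 64.9 − 57.0 = 7.9 points below testing and 8.5 below randomization. If recovery depends on time since onset, the onset clock is 0.4 to 2.9 points better than testing. The inconsistency is certain; its size rests on lags that the documents do not give.

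**What to change.** Before the statistician is unblinded under SAP 7.7, state one origin in identical words in SAP 3.2, SAP 5.3.2 and Protocol 9.4.2. Define every time as the event or censoring date minus that origin date.

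- **Preferred: randomization (Day 1).** It matches the diary, the Day-21 censoring and the randomized comparison, and it removes the guaranteed event-free time. The wording changes in three places. The sizing text in SAP 3.2 and Protocol 9.2 also needs a restated effect assumption and a recomputed power figure, because 16 versus 6 days from onset cannot simply be carried over. Results become less comparable with the onset-based 16 days. Days since onset could enter the Cox model of SAP 5.3.4, at the price of one of its two or three covariate places, if the onset date is recorded.
- **Acceptable smaller repair: symptom onset.** Correct the testing sentence in SAP 3.2 and set censoring time as the Day-21 or off-study date minus the onset date. The sizing medians stand. The onset date must be captured, since Protocol 1.3 and 4.1 do not name it as an item (medical history may hold it), and power may be lower if lags are long. Delayed entry is not advised for a median at this size: at lag 1-14, HR 2 and 26 per arm it raises the SD of the difference in medians from 2.6 to 5.4 days in Model A and from 2.5 to 4.3 days in Model B.

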### 3.2 Sample size

The total sample for this study is a minimum of 52 and up to 60 patients equally split between the placebo arm and the treatment arm.

The sample size is driven by the primary objective to compare the median time to sustained clinical response between the two arms.

For statistical analysis purposes, sustained clinical response is defined as a reduction to a score of <= 2 on all symptom scores on the Modified FLU-PRO Plus questionnaire and remaining <= 2 for

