# BOSS-Covid-19 Study (BOSS-001)

1. To evaluate if treatment with 3 g TQ Formula (500 mg per capsule, 3 capsules BID) given orally on outpatient basis can significantly reduce median time to sustained clinical response compared to placebo in participants with COVID-19 infection treated in the outpatient setting. Sustained clinical response is defined as a reduction of scores to </= 2 on all symptoms of the Modified FLU-PRO Plus and should be remaining </= 2 for at least three days.
2. To evaluate the safety and tolerability of TQ Formula (500 mg oral capsule, 3 capsules BID) when given to participants with COVID-19 infection

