# BOSS-Covid-19 Study (BOSS-001)

## 4 Study Endpoints

### 4.1 Efficacy Endpoints

#### 4.1.1 Primary Efficacy Endpoint:

Measurement of the difference in median time to sustained clinical response in participants taking 3 g TQ Formula (500 mg per capsule, 3 capsules BID) versus participants taking placebo.

Sustained clinical response is defined as a reduction of scores to  $\leq 2$  on all symptoms of the Modified FLU-PRO Plus and sustained  $\leq 2$  for at least three days.

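### The SAP dates the primary endpoint by two incompatible rules, with different score thresholds and different time origins

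*SAP*

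**What the plan says.** **Definition.** SAP 3.2 requires "a reduction to a score of <= 2 on all symptom scores on the Modified FLU-PRO Plus questionnaire and remaining <= 2 for" at least three days. SAP 3.6 repeats the holding period ("and should be remaining </= 2 for at least three days"), and SAP 4.1.1 does the same ("on all symptoms of the Modified FLU-PRO Plus and sustained" at 2 or lower over three days or more).

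**Dating, SAP 3.2.** "Time to sustained clinical response will be calculated from the date of testing to the first day all symptoms are" 2 or lower.

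**Dating, SAP 5.3.2.** Status: "Events will be defined as cases that attain sustained clinical response while on study". Time: "days from the date of symptoms onset to the date that all symptoms are below Level-2 ('A little bit". Censoring: "Patients who do not attain to clinical response while on study will be censored on Day-21", or earlier if the patient leaves the study.

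**Scale.** SAP 7.9 describes the plot axis as 0 to 4, with 'Not at all' at 0, 'Somewhat' at 2 and 'Very much' at 4. Protocol Appendix 2 lists the five answers in order without printed codes. In that order 'A little bit' is Level-1.

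**Planning.** SAP 3.2 also says "the expected median time to response in the placebo arm will be approximately 16 days from the onset of symptoms in outpatients".

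**Protocol.** In the supplied protocol, 9.2 uses 2 or lower, while 9.4.2 measures from onset until symptoms are at zero. SAP 2.2 was written against protocol Version 6.0, so this needs checking against that version. The conflict inside the SAP does not depend on it.

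**The concern.** SAP 5.3.2 is the text a programmer would follow for the primary analysis. It decides who has an event by one threshold and when the event happened by a stricter one, and it starts the clock at a different point from SAP 3.2. Nothing says which section governs. Two careful programmers could produce different event times for the same patients, and some patients would have an event that the survival procedure cannot use without an improvised rule. At stake are the Kaplan-Meier medians and, for some effect sizes, the result of the single primary efficacy test.

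**Working it through.** **1. The plan's own figure.** The SAP states 81.5% power. Inputs: medians 16 and 16 − 10 = 6 days, 20 per arm (SAP 3.2), two-sided 5% (protocol 9.4.1); exponential times are my assumption.

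- Hazard ratio = 16/6 = 2.667.
- Freedman formula, all 40 patients as events: z = √40 × (1.667/3.667) − 1.96 = 0.915, power 82.0%.
- With censoring at 21 days, expected events = 20(1 − 2^(−21/16)) + 20(1 − 2^(−21/6)) = 11.95 + 18.23 = 30.18. Schoenfeld formula: z = (√30.18/2) × ln 2.667 − 1.96 = 0.734, power 76.9%.

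The figure is roughly reproducible. It takes the medians as given, so it cannot settle which dating rule was meant. It does show that the 16 days sits on the onset clock, while the endpoint in the same section starts at testing.

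**2. The threshold, read side by side.**

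| Reading of SAP 5.3.2 | Date falls when every item is |
|---|---|
| Bracket explains 'below Level-2' (agrees with SAP 7.9) | 1 or lower |
| Bracket names Level-2 itself (contradicts SAP 7.9; implies 1–5 coding) | 'Not at all' only |
| SAP 3.2, 3.6, 4.1.1 | 2 or lower |

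Neither reading of the bracket gives 2 or lower.

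**3. The missing date.** Take a patient whose worst item falls to 'Somewhat' on Day 9 and stays there. SAP 3.2 dates the response at Day 9 (converted to days from testing). Under SAP 5.3.2 the patient is an event, but no day through Day 21 satisfies the date rule.

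**4. How often (illustrative).** Assumptions: worst-item score starting uniformly between 3 and 4; linear decline averaging 0.14 points/day, with patient-specific lognormal rates (CV 25–75%); daily noise SD 0.5 or 0.25; scores rounded to 0–4; Days 1–21; no dropout. Rule A is the first day of a three-day run at 2 or lower. Rule B is SAP 5.3.2 taken literally: status from A, date at the first day at 1 or lower, undated responders censored at Day 21.

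- Without noise, one level takes 1/0.14 = 7.1 days. Noise shortens the gap, because rule B needs only one low day.
- Responders with no date: 4–12% (SD 0.5), 9–24% (SD 0.25).
- Dated later than rule A: 73–79% and 75–91%. Median delay where a date exists: 3 and 5–6 days. At SD 0.5 about 6% are dated earlier.
- Log-rank, 26 per arm, 0.14 v 0.20 points/day (rule A medians about 10 v 7 days): verdicts under A and B differ in roughly 12–21% of trials.
- Near the planned effect (0.10 v 0.267 points/day, medians about 12–15 v 6–7 days): about 0–3%, whether the stricter rule is B or a three-day run at 1 or lower. In this model nearly every such trial is significant under every rule, which leaves little room to disagree.

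**5. The origin (illustrative).** Simulated with 20 per arm, exponential medians 16 and 6 days from testing, and censoring at study Day 21. Typical estimated medians are 15 and 6 days on the testing clock. With an assumed mean onset-to-testing gap of 3, 5 or 7 days they become 18/9, 20/12 and 23/14 on the onset clock. Power moves from 77% to 75%, 74% and 73%.

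**The case against.** The best defence is that 'below' was meant loosely as 'at or below', with answers coded 1–5. Level-2 would then be 'A little bit', and the two sections would agree on the threshold. SAP 7.9 rules this out as the text stands, because it puts Level-2 at 'Somewhat' on a 0–4 scale. It is a good reason to print the item codes. It does nothing for the conflict of origins, which needs no interpretation.

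Several stronger readings are tempting and should not be drawn:

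- *That most responders will be dated late.* This comes from the assumed linear model. SAP 5.3.2 does not even say 'first' day.
- *That power is lost.* In the worst-item model the stricter rules tend to have more power (CV 50%, SD 0.5: 47% under A, 54% under B). If the stricter end is instead modelled as a random extra lag of 1–7 days on exponential times, power falls from 77% to 76–55%. The sign depends on the model.
- *That the type I error rate is inflated.* Any one rule fixed in advance is valid; with equal arms each gave 4.5–6.1% significant.
- *That the rule would be picked after unblinding.* SAP 7.7 unblinds the study statistician for the preliminary efficacy analysis, after the efficacy data are checked and locked. It does not say that event dates are defined then.
- *That Day-21 censoring has no clock.* It is a study date, and the time to it from either origin follows by subtraction.
- *That carried-forward diary values are unaddressed.* SAP 7.1 applies last-value-carried-forward to intermittent gaps in this questionnaire, so the natural reading is that they feed the derivation.

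**Conclusion.** The contradiction is real and lies wholly within the current SAP. The primary endpoint has two thresholds for its date (2 or lower against 1 or lower) and two origins (testing against onset). SAP 5.3.2 taken literally leaves some responders with an event and no date. That conclusion rests on the text alone, and it must be fixed because it concerns the single primary efficacy test.

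The size is not known from the documents. Under the stated assumptions about 4–24% of responders would be undated. The test result would depend on the rule in roughly 12–21% of trials at a modest effect, but hardly ever near the planned one. The conflict of origins is secondary: it mainly moves the reported medians by the onset-to-testing gap, which the documents do not give.

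**What to change.** Before the efficacy lock and unblinding:

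1. In SAP 5.3.2, replace the 'below Level-2' wording with the SAP 3.2 rule made explicit: the event date is the first day of a run of at least three consecutive days with every item at 2 or lower on the 0–4 coding of SAP 7.9. Print the item codes.
2. Say 'of the run' in SAP 3.2 too. In the model above, 46–75% of responders have an isolated day at 2 or lower before the qualifying run.
3. Use one time origin in SAP 3.2 and 5.3.2, and measure Day-21 censoring from it.
4. Confirm in one sentence that carried-forward diary days count toward the run (minor).
5. Correct the zero-symptom rule in protocol 9.4.2 if it is still in the current version.

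No new data are needed. If the chosen origin is not symptom onset, the basis of the 16-day planning median and the power statement must be restated. If 1 or lower was intended, that is a different endpoint: 28–42% of responders in the model have no three-day run at that level. SAP 3.2, 3.6 and 4.1.1 and the power basis would then have to change instead.
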